5.3. Lifestyle Considerations

In relation to IMP administration, subjects should adhere to meals and dietary restrictions regarding food intake:

- No food intake for 2 hours prior to taking the IMP.
- No food intake for 1 hour after taking the IMP.

5.4. Screen Failures

A screen failure occurs when a subject who consents to participate in the clinical trial is not subsequently randomly assigned to IMP. A minimal set of screen failure information is required to ensure transparent reporting of screen failure subjects to meet the Consolidated Standards of Reporting Trials publishing requirements and to respond to queries from regulatory authorities. Minimal information includes demography, screen failure details, eligibility criteria, and any SAE. Individuals who do not meet the criteria for participation in this trial (screen failure) must not be rescreened.

6. Investigational Medicinal Product and Concomitant Therapy

The IMP is the active (C21) or placebo treatment intended to be administered to a trial subject according to the trial protocol.

6.1. Investigational Medicinal Product Administered

Each subject will be randomized to receive treatment with the IMP (C21 or placebo). The IMP will be administered as a capsule for oral administration. Each subject will receive 4 capsules per day, divided in 2 doses given twice a day.

IMP will be administered in fasting conditions (see Section 5.3). C21 is an AT2R agonist. The drug substance is 3-[4-(1H-imidazol-1-ylmethyl)phenyl]-5-(2-methylpropyl)thiophene-2-[(N-butyloxylcarbamate)-sulphonamide] sodium salt supplied as a free form equivalent (eq.) 50 mg C21 oral capsule.

Table 1. Investigational Medicinal Product Administered

IMP Name	Active / C21	Placebo
Dose Formulation	Capsule	Capsule
Unit Dose Strength(s)	52.3 mg pr capsule	Placebo
Dosage Level(s)	2 capsules, b.i.d.	2 capsules, b.i.d.
Excipients	Mannitol, Anhydrous colloidal silica, Magnesium stearate	Mannitol, Anhydrous colloidal silica, Magnesium stearate
Capsule	Vcaps® plus	Vcaps® plus
Route of Administration	Oral	Oral
Dosage description	Subjects will receive 100 mg C21 b.i.d. on Day 1 to Day 14.	Subjects will receive Placebo b.i.d. on Day 1 to Day 14.
Sourcing	Provided centrally by the sponsor	Provided centrally by the sponsor
Packaging and Labeling	IMP will be provided in a container. Each container will be labeled as required per country requirement.	IMP will be provided in a container. Each container will be labeled as required per country requirement.

6.2. Preparation, Handling, Storage, and Accountability

- The investigator or designee must confirm appropriate temperature conditions have been maintained during transit for all IMP received, and any discrepancies are reported and resolved before use of the IMP.
- Only subjects enrolled in the trial may receive IMP, and only authorized site staff may supply or administer IMP during hospitalization. Prior to dispensing, all IMP must be stored at 15 to 25 °C (59-77°F) in a secure, environmentally controlled, and monitored (manual or automated) area in accordance with the labeled storage conditions with access limited to the investigator and authorized site staff.

- If a subject is discharged from the hospital prior to Day 15, IMP accountability will be performed, and the subject will be instructed to self-administer the remaining IMP at home. The subject must be instructed to store IMP at room temperature (15-25°C, 59-77°F). The IMP should be kept in the plastic container until intake, out of reach from children.
- In subjects where oral intake becomes a significant challenge e.g., during invasive mechanical ventilation or ECMO treatment, IMP will be administered as a dispersion, either orally or via a nasogastric or nasoenteral feeding tube. It may also include situations in which nasogastric or nasoenteral tube feeding may become required, such as non-invasive mechanical ventilation, high flow oxygen therapy and gastric/oesophageal discomfort. Route of administration will be collected in the eCRF.
- The subject should return all used and unused IMP at Visit 16 (Day 15) or at the EWD visit for subject withdrawing prior to Visit 16.
- The investigator and the pharmacy (if applicable) are responsible for IMP accountability, reconciliation, and record maintenance (i.e., receipt, reconciliation, and final disposition records).

Further guidance and information on preparation, handling, storage, and accountability are provided in the IMP handling manual.

6.3. Measures to Minimize Bias: Randomization and Blinding

This is a double-blind trial in which subjects, care providers, investigators, outcomes assessors, sponsor and CRO/vendor staff are blinded to IMP allocation i.e., intervention assignment. The interactive web response system will be programmed with blind-breaking instructions.

In case of an emergency, the investigator has the sole responsibility for determining if unblinding of a subjects' intervention assignment is warranted. Subject safety must always be the first consideration in making such a determination. If the investigator decides that unblinding is warranted, the investigator should make every effort to contact the sponsor prior to unblinding a subject's intervention assignment unless this could delay emergency treatment for the subject. If a subject's intervention assignment is unblinded, the sponsor must be notified within 24 hours of this occurrence. The date and reason for the unblinding must be recorded.

Sponsor pharmacovigilance staff or the pharmacovigilance vendor appointed by the sponsor may unblind the intervention assignment for any subject with an SAE. If the SAE requires that an expedited regulatory report be sent to one or more regulatory agencies, a copy of the report, identifying the subject's intervention assignment, may be sent to investigators in accordance with local regulations and/or sponsor policy. A blinding plan will describe any unblinded sponsor, or CRO/vendor staff during the conduct of the trial.

6.4. Investigational Medicinal Product Compliance

When subjects are randomized at the site, they will receive the IMP doses directly from the investigator or designee, under medical supervision. The date and time of each dose administered in the clinic will be recorded in the source documents. The IMP container number and trial

subject identification will be confirmed at the time of dosing by a member of the trial site staff other than the person dispensing the IMP.

During the hospitalization, the investigator or designee should investigate and document if the fasting criteria for the IMP (see Section 5.3) has been fulfilled.

If a subject is discharged from the hospital prior to Day 15 and self-administer the remaining IMP at home, IMP compliance and compliance with fasting criteria will be assessed at Visit 16 (Day 15) and documented in the source documents and the eCRF relevant form. Deviation(s) from the prescribed dosage regimen and fasting criteria should be recorded.

A record of the quantity of IMP dispensed to and administered by each subject must be maintained and reconciled with IMP and compliance records. Intervention start and stop dates, including dates for intervention delays and/or dose reductions will also be recorded.

6.5. Dose Modification

Dose modifications during the 14-day IMP treatment period are not allowed.

6.6. Continued Access to the Investigational Medicinal Product after End of Trial

There will not be continued access to the IMP after end of treatment (Day 15).

6.7. Treatment of Overdose

In this trial, any dose of C21 exceeding a total daily dose of 200 mg (i.e., 4 capsules of IMP) is considered an overdose.

Sponsor does not recommend any specific treatment for an overdose.

In the event of an overdose, the investigator should:

- Evaluate the subject to determine, in consultation with the medical monitor, whether IMP treatment should be interrupted.
- Closely monitor the subject for any AE/SAE and laboratory abnormalities.
- Document the quantity of the excess dose as well as the duration of the overdose.

Overdoses should be reported as an AE.

6.8. Prior and Concomitant Therapy

Concomitant therapy is defined as any medication or vaccine (including over-the-counter, prescription medicines, recreational drugs, vitamins, and/or herbal supplements) or other specific categories of interest that the subject is receiving at the time of enrollment or receives during the trial.

SoC for COVID-19 as described in Appendix 4 should be applied during the trial.

All concomitant therapy and prior therapy taken up to 4 weeks prior screening (Visit 1) should be recorded. The investigator must obtain information on medications and therapies for the COVID-19 related infections for each subject.

Other relevant prior therapy as judged by the investigator will be collected and recorded.

Concomitant therapy and prior therapy must be recorded along with:

- Reason for use.
- Dates of administration including start and end dates.
- Dosage information including dose and frequency.

The medical monitor should be contacted if there are any questions regarding concomitant or prior therapy.

COVID-19 vaccination is allowed prior to screening (Visit 1) and after the end of the IMP treatment period (Day 15). Vaccination for COVID-19 during the IMP treatment period is prohibited. COVID-19 vaccinations should be recorded in the eCRF. Treatment with the following prohibited medication is not allowed from 1 week prior to screening (Visit 1) and until Day 15 (Visit 16):

- a. Strong Cytochrome P450 (CYP) 3A4 inducers
- b. P-glycoprotein (P-gp) substrates with narrow therapeutic index
- c. High dose BCRP sensitive substrates
- d. Warfarin
- e. Sulphasalazine or rosuvastatin

Strong Cytochrome P450 (CYP) 3A4 inducers, P-glycoprotein (P-gp) substrates with narrow therapeutic index and high dose BCRP sensitive substrates considered prohibited medication include drugs listed in the FDA tables of substrates, inhibitors and inducers for drug development and drug interactions ([FDA, 2020b](#)).

7. Discontinuation of Investigational Medicinal Product and Subject Discontinuation/Withdrawal

Discontinuation of specific sites or of the trial are detailed in Appendix 1 (see Section 10.1).

7.1. Discontinuation of Investigational Medicinal Product

A subject should be withdrawn from the IMP treatment if it in the opinion of the investigator is medically necessary or if it is the wish of the subject.

If IMP treatment is discontinued, the date of last IMP administration and the date and reason for treatment withdrawal should be reported in the eCRF. If a subject is removed from treatment because of an AE, the reason for treatment withdrawal should always be stated as 'adverse event' irrespective of whether this was the investigator's or the subject's decision.

If IMP treatment is discontinued, the investigator should make all efforts to ensure that the subject will remain in the trial and ensure that the subject attends the remaining visits in the trial.

IMP treatment should be discontinued in case of drug induced liver injury according to criteria specified in FDA guidance ([FDA, 2009](#)), moderate or severe impairment of hepatic function (e.g., Child-Pugh class B or C where alterations in the score components are not due to another underlying disease (see Section 8.4.5)), or severe renal impairment (i.e., estimated glomerular filtration rate (eGFR) ≤ 30 ml/min/1.73 m²).

7.1.1. Temporary Discontinuation

There are no specific criteria for temporary discontinuation of IMP treatment. If temporary discontinuation of IMP is required according to investigator's judgement, the date and reason for a temporary discontinuation should be reported in the eCRF. If the subject is still within the treatment period of the trial when a temporary discontinuation is no longer required, IMP treatment can be restarted.

7.2. Subject Discontinuation/Withdrawal from the Trial

- A subject may withdraw from the trial at any time at his/her own request i.e., withdrawal of consent.
- At the time of discontinuing from the trial, if possible, an EWD visit should be conducted, as described in the SoA.
- The subject will be permanently discontinued from the IMP at the time of withdrawal from the trial.
- If the subject withdraws consent for disclosure of future information, the sponsor may retain and continue to use any data collected before such a withdrawal of consent.
- If a subject withdraws from the trial, he/she may request destruction of any samples taken and not tested, and the investigator must document this in the site trial records.

7.3. Lost to Follow up

A subject will be considered lost to follow-up if he/she repeatedly fails to return for scheduled visits and is unable to be contacted by the trial site.

The following actions must be taken if a subject fails to return to the clinic for a required trial visit:

- The site must attempt to contact the subject and reschedule the missed visit as soon as possible, counsel the subject on the importance of maintaining the assigned visit schedule and ascertain whether the subject wishes to and/or should continue in the trial.
- Before a subject is deemed lost to follow-up, the investigator or designee must make every effort to regain contact with the subject (where possible, 3 telephone calls, and if necessary, a certified letter to the subject's last known mailing address or local equivalent methods). These contact attempts should be documented in the subject's medical record.
- Should the subject continue to be unreachable, he/she will be considered to have withdrawn from the trial.

8. Trial Assessments and Procedures

- Trial procedures and their timing are summarized in the SoA. Protocol waivers or exemptions are not allowed.
- Immediate safety concerns should be discussed with the sponsor or designee immediately upon occurrence or awareness to determine if the subject should continue or discontinue IMP.
- Adherence to the trial design requirements, including those specified in the SoA, is essential and required for trial conduct.
- All screening evaluations must be completed and reviewed to confirm that potential subjects meet all eligibility criteria. The investigator will maintain a screening log to record details of all subjects screened and to confirm eligibility or record reasons for screening failure, as applicable.
- Procedures conducted as part of the subject's routine clinical management (e.g., PCR tests for SARS-CoV-2 collected less than 3 days prior to Visit 2 (or less than 7 days prior to Visit 2 in case of documented inability to obtain a repeat sample and progressive disease suggestive of ongoing SARS-CoV-2 infection)) and obtained before signing of the ICF may be utilized for screening or baseline purposes provided the procedures met the protocol-specified criteria and were performed within the timeframe defined in the SoA.

The maximum amount of blood collected from each subject over the duration of the trial, including any extra assessments that may be required, will not exceed 130 mL.

8.1. Screening Assessments

Planned timepoints for all screening assessments are provided in the SoA. Screening procedures may be done over 1 to 2 calendar days.

8.1.1. Demographics

Demographic and baseline characteristics will be obtained. This following information will be collected:

- Age at screening
- Race and ethnicity
- Sex
- Height
- Body weight

8.1.2. Medical History

All current medical conditions and relevant previous medical conditions according to investigator judgement should be recorded.

The medical history should include the following information:

- Date of onset of COVID-19 signs and symptoms.
- Date of COVID-19 diagnosis (defined as sample date for positive COVID-19 PCR test).
- History of chronic medical conditions including chronic supplemental oxygen requirement prior to onset of COVID-19 signs and symptoms.
- History of previous COVID-19 diagnosis and serology results (if relevant and known).

8.2. Efficacy Assessments

Planned timepoints for all efficacy assessments are provided in the SoA.

8.2.1. 8-point Ordinal Scale

The clinical status of COVID-19 is scored at each visit according to the 8-point ordinal scale ([Beigel et al., 2020](#)), which is an investigator evaluation of the clinical status at the first assessment of a given trial day. The clinical status of COVID-19 according to the 8-point ordinal scale must further be scored at the time of hospital discharge. For subjects hospitalized between Day 29 (Visit 31) and Day 60 (Visit 32), the clinical status of COVID-19 should be scored each time a change in clinical COVID-19 status is seen and until hospital discharge.

The 8-point ordinal scale is as follows:

1.	Not hospitalized, no limitations on activities
2.	Not hospitalized, limitation on activities and/or requiring home oxygen
3.	Hospitalized, not requiring supplemental oxygen - no longer requires ongoing medical care
4.	Hospitalized, not requiring supplemental oxygen - requiring ongoing medical care (COVID-19-related or otherwise)
5.	Hospitalized, requiring supplemental oxygen
6.	Hospitalized, on non-invasive ventilation or high flow oxygen devices
7.	Hospitalized, on invasive mechanical ventilation or ECMO
8.	Death

A subject re-admitted to the hospital for a non-COVID-19 related reason should be considered not hospitalized when scoring the clinical status of COVID-19 on the 8-point ordinal scale.

8.2.2. Supplemental Oxygen

Any daily need for supplemental oxygen will be recorded at each visit from screening (Visit 1) to Day 29. This will include use of supplemental oxygen during hospitalization and at home.

8.2.3. Oxygen Saturation

- Resting peripheral capillary oxygen saturation (SpO₂) will be performed as outlined in the SoA.
- SpO₂ recording should be preceded by at least 5 minutes of rest for the subject in a quiet setting.
- SpO₂ will be recorded up to 2 times with a 5-minute interval between the measurements.
- Supplemental oxygen flow rate (L/min), oxygen delivery device, FiO₂, airway pressure, if applicable, must be assessed at the time of measuring SpO₂.

8.3. Survival and Hospitalization

Data on survival, hospital discharge and hospital re-admissions will be collected at each visit from Day 2 (Visit 3) to Day 60 (end-of-trial). Information on the hospital setting, including intensive care unit (ICU), high flow oxygen device use, ventilator use (Non-invasive, Invasive or ECMO) will be collected.

8.4. Safety Assessments

Planned timepoints for all safety assessments are provided in the SoA (see Section 1.3).

8.4.1. Physical Examinations

- Physical examinations will be performed as outlined in the SoA (see Section 1.3).
- The physical examination will include assessments of the respiratory and cardiovascular systems. Other systems will be assessed per investigator judgment.
- Investigators should pay special attention to clinical signs related to previous serious illnesses.
- Each body system will be reported as “normal” or “abnormal”. Any clinically significant abnormalities prior to initiation of IMP should be specified and recorded as medical history. New clinically significant abnormalities occurring after initiation of IMP should be reported as AEs.

8.4.2. Vital Signs

- Body temperature, pulse rate, respiratory rate and blood pressure will be measured as outlined in the SOA (see Section 1.3).
- Blood pressure, respiratory rate and pulse measurements should be preceded by at least 5 minutes of rest for the subject in a quiet setting without distractions (e.g., television, cell phones).
- Vital signs (to be taken before blood collection for laboratory tests) will consist of 1 pulse and 3 blood pressure measurements (3 consecutive blood pressure readings will be recorded at intervals of at least 1 minute).

- Any clinically significant abnormalities prior to initiation of IMP should be specified and recorded as medical history. New clinically significant abnormalities occurring after initiation of IMP should be reported as AEs.

8.4.3. *Electrocardiograms*

- 12-lead electrocardiograms (ECGs) will be obtained as outlined in the SoA (see Section 1.3) using local ECG equipment that automatically calculates the heart rate and measures PR, QRS, QT, and QTcF intervals.
- Historical 12-lead ECGs are acceptable if ≤ 2 days old at the time of screening (Visit 1).
- The ECG assessment will be reported as “normal” or “abnormal”. Any clinically significant abnormalities should be specified and recorded as medical history.

8.4.4. *Clinical Safety Laboratory Tests*

- Blood and urine samples for clinical safety laboratory tests will be collected as outlined in the SoA (see Section 1.3). Samples collected at screening (Visit 1) will be analyzed using local laboratories and used to confirm eligibility for participation in the trial.
- Day 1 (Visit 2), samples will be collected before IMP administration.
- Samples collected at all other visits will be analyzed by the central laboratory.
- If needed due to special circumstances e.g., delays in turn-around time due to COVID-19, blood samples may be analyzed locally after sponsor approval.
- The tests detailed in [Table 2](#) will be performed.

Table 2. Protocol-required Safety Laboratory Tests

Laboratory Tests	Parameters	
Hematology	Platelet count (thrombocytic particle concentration) Hemoglobin Hematocrit (erythrocyte volume fraction) Mean corpuscular volume (MCV)	White blood cell (WBC) count with differential: Neutrophils Lymphocytes Monocytes Eosinophils Basophils
Clinical chemistry	Blood urea nitrogen (BUN) Glucose, fasting Potassium Sodium Calcium Ferritin Prothrombin time (PT) International Normalized Ratio (INR) activated partial thromboplastin time (aPTT)	AST Alanine transferase (ALT) Alkaline phosphatase (ALP) Albumin Total and direct bilirubin Serum creatinine eGFR CRP LDH
Routine urinalysis	
 pH, glucose, protein, ketones, bilirubin, urobilinogen, and specific gravity by dipstick Microscopic examination (per investigator judgment) 	
Pregnancy testing	
 Highly sensitive urine or serum human chorionic gonadotropin pregnancy test (as needed for women of childbearing potential) 	

- Investigators must review of each laboratory safety report. Any clinically significant abnormalities at screening (Visit 1) or Day 1 (Visit 2) will be reported as medical history. New clinically significant abnormalities after Day 1 (Visit 2) should be reported as AEs.

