1.2. Schema

1.3. Schedule of Activities (SoA)

	Screening	IMP Treatment Period				In-patient Stay ¹⁾	Follow-up Period ²⁾			Unscheduled ³⁾
Visit	V1	V2	V3-15 ^{1,4)}	V16 ⁴⁾	EWD ⁵⁾	V17-29	V30	V31	V32	UV
Day (Visit window)	Up to 48h prior to V2	Day 1	Days 2-14	Day 15 (+1 day)		Days 16-28	Day 22 (±1 days)	Day 29 (±1 days)	Day 60 (±3 days)	
Eligibility/General										
Informed consent	X									
Eligibility criteria	X	x ⁶⁾								
Demographics	X									
Medical history	X									
IMP and Concomitant Therapy										
Randomization		x								
IMP administration ⁷⁾		x	x							(x)
Check of fasting criteria		x	x							(x)
IMP accountability			x ⁸⁾	x	x					
Previous and concomitant therapy	X	x	x	x	x	x	x	x		(x)
Trial Assessments and Procedures										
8-point ordinal scale	X	x	x	x	x	x	x	x	x	(x)
Supplemental O ₂	X	x	x	x	x	x	x	x	x	(x)
Oxygen saturation	X	x	x	x	x	x				(x)
Hospitalization	X	x	x	x	x	x	x	x	x	(x)
Physical examination	X			x	x					(x)
Body weight and height	X									
Vital signs	X	x	x	x	x	x				(x)
12-lead ECG ⁹⁾	X									(x)
Adverse events	X	x	x	x	x	x	x	x	x ¹⁰⁾	x
Biochemistry ¹¹⁾	X	x ¹²⁾	Days 3, 5, 8, 11 (all ± 1 day)	x	x					(x)
Haematology ¹¹⁾	X	x ¹²⁾	Days 3, 5, 8, 11 (all ± 1 day)	x	x					(x)
Urinanalysis ¹¹⁾	X	x ¹²⁾		x	x					(x)
Pregnancy testing ¹³⁾	X			x	x					(x)
Oropharyngeal swab		x								
Pharmacokinetics ¹⁴⁾		x								
Blood sample for future exploratory analysis		x ¹²⁾		x	x					

1. Daily visits until discharge. Visits will be re-initiated in case of a COVID-19 related hospital re-admission.
2. Follow-up visits by phone or video.
3. Assessments marked with () will be performed per investigator judgment at e.g., COVID-19 related hospital re-admission after Day 29.
4. Days 8 and 15 visits must be performed for all subjects. If a subject is discharged before Day 8, the Day 8 visit will be done by phone or video. Site assessments e.g., oxygen saturation, vital signs and blood sampling will not be performed.
5. An early withdrawal (EWD) visit should be performed for subjects withdrawn from the trial prior to Day 15 (Visit 16).
6. Re-evaluation of eligibility including evaluation of electrocardiogram (ECG) and laboratory results from screening.
7. IMP is administered b.i.d. from Days 1 to 14.
8. IMP accountability will be performed at hospital discharge.
9. A historical 12-lead ECG is acceptable. The ECG should be ≤2 days old at the time of screening (Visit 1).
10. SAEs only.

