8.5. Adverse Events, Serious Adverse Events, and Other Safety Reporting

The definitions of AEs and SAEs can be found in Appendix 2 (see Section 10.2).

AEs will be reported by the subject (or, when appropriate, by a caregiver, surrogate, or the subject's legally authorized representative).

The investigator and any qualified designees are responsible for detecting, documenting, and recording events that meet the definition of an AE or SAE and remain responsible for following up all AEs OR AEs that are serious, considered related to the IMP or trial procedures, or that caused the subject to discontinue the IMP or trial (see Section 7).

The method of recording, evaluating, and assessing causality of AEs and SAEs and the procedures for completing and transmitting SAE reports are provided in Appendix 2 (see Section 10.2).

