10.2.1. Definition of AE

AE Definition

• An AE is any untoward medical occurrence in a clinical trial subject, temporally associated with the use of IMP, whether or not considered related to the IMP.• NOTE: An AE can therefore be any unfavorable and unintended sign (including an abnormal laboratory finding), symptom, or disease (new or exacerbated) temporally associated with the use of IMP.
Events Meeting the AE Definition

• Any abnormal laboratory test results (hematology, clinical chemistry, or urinalysis) or other safety assessments (e.g., ECG, radiological scans, vital signs measurements), including those that worsen from baseline, considered clinically significant in the medical and scientific judgment of the investigator (i.e., not related to progression of underlying disease).• Exacerbation of a chronic or intermittent pre-existing condition including either an increase in frequency and/or intensity of the condition.• New condition detected or diagnosed after IMP administration even though it may have been present before the start of the trial.• Signs, symptoms, or the clinical sequelae of a suspected intervention-intervention interaction.• Signs, symptoms, or the clinical sequelae of a suspected overdose of either IMP or a concomitant therapy. Overdose to be reported as an AE/SAE.• Lack of efficacy or failure of expected pharmacological action per se will not be reported as an AE or SAE. Such instances will be captured in the efficacy assessments. However, the signs, symptoms, and/or clinical sequelae resulting from lack of efficacy will be reported as AE or SAE if they fulfill the definition of an AE or SAE.
Events NOT Meeting the AE Definition

• Medical or surgical procedure (e.g., endoscopy, appendectomy): the condition that leads to the procedure is the AE.• Situations in which an untoward medical occurrence did not occur (social and/or convenience admission to a hospital).• Anticipated day-to-day fluctuations of pre-existing disease(s) or condition(s) present or detected at the start of the trial that do not worsen.

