12.6.5 Physical Examinations, ECGs, and Other Observations Related to Safety

The physical examination system will be summarized as "normal", "abnormal" with sub category for abnormal events that are clinically significant and the number and percentages of subjects in each category by body system will be presented by time point and treatment group in SS. The assessment of the exam is as reported in the Physical Examination (Body System) CRF page. All physical examination data will be listed.

ECG will only be performed at screening and unscheduled visits. ECG will be summarized for screening, unscheduled visits and "any post-baseline assessment" by treatment group in the SS.

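### Protocol 8.4.3 sends every clinically significant ECG abnormality to medical history with no time limit, which conflicts with the AE definition in 10.2.1 for ECGs taken after dosing

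*Protocol*

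**What the plan says.** The Schedule of Activities (Protocol 1.3) marks the 12-lead ECG at screening and, in brackets, at unscheduled visits. Its footnote explains the brackets: "Assessments marked with () will be performed per investigator judgment at e.g., COVID-19 related hospital re-admission after Day 29". SAP 12.6.5 repeats the schedule ("ECG will only be performed at screening and unscheduled visits") and plans a summary by treatment group for screening, unscheduled visits and any post-baseline assessment.

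Protocol 8.4.3 states that ECGs are obtained according to that schedule and accepts recent historical ECGs at screening. It ends with the recording rule: "Any clinically significant abnormalities should be specified and recorded as medical history".

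Protocol 8.5 directs the reader elsewhere for what counts as an AE: "The definitions of AEs and SAEs can be found in Appendix 2 (see Section 10.2". There, 10.2.1 includes abnormal results from "other safety assessments (e.g., ECG, radiological scans, vital signs measurements), including those that worsen from baseline, considered clinically significant" in the investigator's judgment.

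**The concern.** For an ECG taken after the first dose, 8.4.3 and 10.2.1 give different instructions. The first makes a clinically significant abnormality medical history; the second makes it an AE. I found no statement of which prevails, and 8.4.3 is the ECG-specific section that site staff would naturally consult.

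What is at stake is completeness of the AE data. SAP 12.6.1 builds its AE summaries, and the risk differences with 95% confidence intervals, from treatment-emergent AEs. Medical history is summarized in SAP 12.2 with demographic and baseline characteristics. An on-treatment finding entered only as medical history would miss the first and could appear in the second as if it had been present at entry. It would also carry none of the severity and causality grading that an AE record requires. With no scheduled ECG after screening, few other places in the data would show it.

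**Working it through.** The point is textual; no sample size, rate or error level enters, so there is nothing to calculate. The check sets the rules side by side and follows one finding through each.

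**Step 1: does 8.4.3 reach post-dose ECGs?** Yes. It covers ECGs according to the Schedule of Activities, which includes the unscheduled column. That column also has bracketed entries for IMP administration and the fasting check, so unscheduled visits during treatment are foreseen. The footnote's own example, re-admission after Day 29, falls after dosing. SAP 12.6.5 plans for post-baseline ECGs.

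**Step 2: compare the recording rules.**

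| Assessment | Before or at start of IMP | New finding afterwards |
|---|---|---|
| Physical examination (8.4.1) | Medical history | "New clinically significant abnormalities occurring after initiation of IMP should be reported as AEs" |
| Vital signs (8.4.2) | Medical history | AE, same rule as 8.4.1 |
| Laboratory tests (8.4.4) | Medical history (screening or Day 1) | "New clinically significant abnormalities after Day 1 (Visit 2) should be reported as AEs" |
| ECG (8.4.3) | Medical history | Medical history, read literally |
| AE definition (10.2.1) | Not addressed | AE, with ECG named |

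The ECG row is the only one without a split in time, and its last cell contradicts the row below it.

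**Step 3: follow a new, clinically significant, non-serious abnormality on an unscheduled ECG on Day 10.**

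- *Site applies 10.2.1:* it is reported as an AE. It starts after first dose, so SAP 10.6 makes it treatment-emergent and SAP 12.6.1 tabulates it.
- *Site applies 8.4.3 literally:* it is entered as medical history. No AE record exists, so SAP 10.6 has nothing to classify and the finding is absent from the 12.6.1 tables. If the ECG itself was entered in the CRF, it should still appear in the 12.6.5 summary by arm, as an ECG result and not as an AE.

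**Step 4: limits.** Protocol 8.5.1 collects all AEs to Day 29 and only SAEs from then to Day 60, so for non-serious findings the conflict matters from first dose to Day 29. Protocol 10.2.1 also excludes findings attributed to progression of the underlying disease, so some post-dose ECG findings would not be AEs under either rule.

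**The case against.** The best defence is that 8.4.3 describes the screening ECG. Screening is the only scheduled ECG, the preceding bullet concerns historical ECGs at Visit 1, and medical history is marked in the Schedule of Activities only at Visit 1 and described in 8.1.2 under screening assessments. This probably explains how the bullet came to be written. It does not settle the matter, because the bullet does not limit itself to screening and the section covers unscheduled ECGs as well.

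The second defence is that other rules protect the AE data. Section 10.2.1 names ECG. Protocol 8.5.1 requires every SAE to be reported within 24 hours of awareness, with no exception for ECG findings. Protocol 10.2.3 asks for the diagnosis where possible instead of the isolated sign, so a diagnosed cardiac event should be reported as such. SAP 12.6.5 is a further safeguard. All of this stands, and it limits the consequence to what a site could do in error.

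A reader might infer more: that post-dose ECG abnormalities are bound to be absent from the AE tables, or that the route to SAE reporting and the DMC is shut. The documents do not support either, for the reasons just given. A reader might also take SAP 12.6.5 to compare screening with post-baseline ECGs despite unequal coverage. It lists these as separate categories by arm and plans no change from baseline, shift table or test for ECG.

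**Conclusion.** The conflict is real and the 8.4.3 rule is wrong as written for ECGs taken after dosing. The consequence is a risk of misfiling: a non-serious on-treatment ECG finding could be recorded as medical history at some sites and as an AE at others, and in the first case would be left out of the treatment-emergent AE tables and risk differences.

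The size cannot be stated. Neither document gives an expected number of unscheduled ECGs or of new abnormalities among them, and only the latter could be affected. The conclusion rests on two assumptions: that some unscheduled ECGs are taken after first dose, which both documents allow, and that some sites follow 8.4.3 without turning to Appendix 2. The primary and key secondary efficacy analyses are untouched. The absence of scheduled on-treatment ECGs is a separate design choice and is not criticized here.

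**What to change.** Reconcile 8.4.3 with 10.2.1 by giving its last bullet the wording of 8.4.1 and 8.4.2: clinically significant ECG abnormalities found before the first IMP intake are recorded as medical history; new ones after IMP has started are reported as AEs, within the collection periods of 8.5.1. An amendment or a memo to sites would do.

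Two optional additions, before database lock: check each abnormal post-baseline ECG against the subject's AE records and query any without a match, and show in the SAP 12.6.5 table how many post-baseline ECGs were performed in each arm.

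The cost is one sentence, a short blinded data check and one extra row in a table. No ECG, visit or change in patient management is added.
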